Short duration of dual antiplatelet therapy with Synergy® II everolimus eluting stent in patients Older than 75 years undergoing percutaneous coronary Revascularization. The SENIOR trial.

Protocol number: 10-389

Version: 13.0

Dated on: 14 JAN 2014

Principal Investigators

[name]

Hôpital Cochin.

Paris -France

Co-Principal Investigators

[name]

KU Leuven

Leuven - Belgium

[name]

Hôpital La Timone

Marseille– France

Planned Number of Sites and Region

Around 40 sites in approximately 8 European countries including (but not limited to) Belgium, Finland, France, Latvia, Spain, Sweden, Switzerland and United Kingdom.

Sponsor

CERIC

[name]

[name]–

Switzerland

Trial Type:

Randomized Clinical Trial. Prospective, single blinded, randomized multicenter trial of 1,200 patients ≥ 75 years with significant coronary artery disease requiring percutaneous coronary intervention for stable angina, silent ischemia or acute coronary syndrome. Patients will be randomized to receive either a latest generation drug eluting stent with a bioresorbable polymer or a bare metal stent. Dual antiplatelet duration will be short and similar between the two groups of patients.

Data Monitoring:

CERC

[name]

France

Data Analysis:

CERC

[name]

France

Angiographic Core Laboratory only for end point related events

CERC

[name]

France

Electronic Data Capture:

CLINIGRID

[name]

France

Quality of Life evaluation

[name], PhD

Hôpital Broca – La Rochefoucault - [name]

France

Cost-effectiveness evaluation

[name], PhD

Hôpital de l'Hôtel Dieu - [name]

France

Randomization Service(web based)

CLINIGRID

[name]

France

Scientific Committee

[name], [name], [name], [name] and [name].

Clinical Events Committee

[name], [name], [name], [name], [name], [name].

Data Safety Monitoring Board

[name] (president), [name], [name].

Statistical analysis

[name], PhD

Group Biomedical Sciences

Dept. Public Health and Critical Care

Interuniversity Centre for Biostatistics and Statistical Bioinformatics

[name]

Belgium

Clinical Investigation Plan(CIP) Signature Page

Study name	SENIOR Trial

17.5-Data collection and handling.....	34
17.6- Confidentiality and data protection.....	35
17.7-Archiving of documents and data collected	35
17.8- Financing and Insurance.....	35
17.9- Publication policy.....	36
18- Study responsibilities	36
18.1-Sponsor responsibilities	36
18.2- Investigator responsibilities	36
18.3- Monitor responsibilities	39
19-Appendix: definitions, abbreviations and acronyms	39
19-1 Primary endpoint definition	39
19-1-1 Definition of Death	39
19-1-2 Definition of Acute Myocardial infarction(7)	43
19-1-3 Definition of coronary revascularization procedures	46
19-1-4 Other definitions.....	48
20.References	55
21APPENDIX: Role of the Funding source	57
22.Medico-economic study	59
Medico economic evaluation of the SENIOR study:	59
Economic evaluation	59
Costs	60
Health Outcomes	61
Statistical Analysis	61

Protocol Summary

Trial Name	SENIOR trial Short duration of dual antiplatelet therapy with Synergy [®] II everolimus eluting stent in patients older than 75 years undergoing percutaneous coronary revascularization.
Objectives	
 - To establish the efficacy and safety of the Synergy[®] II everolimus eluting stent with abluminal biodegradable polymer (EESabp) associated with a short dual antiplatelet therapy in patients ≥ 75 years old, suffering from stable angina, silent ischemia or acute coronary syndromes related to significant coronary artery disease and requiring percutaneous coronary intervention. - To demonstrate that EESabp in patients ≥ 75 years old is associated with a lower rate of the composite of all-cause mortality, myocardial infarction, stroke or ischemia driven target lesion revascularization (efficacy) and a similar risk of major bleeding (safety) than bare metal stent at an anticipated median follow-duration of one year.
Study devices	
-everolimus eluting stents (Synergy[®] II stents):
 
 2.25 mm x 8, 12, 20, 28, 32, 38 mm 2.50 mm x 8, 12, 20, 28, 38 mm 3.00 mm x 8, 12, 20, 28, 38 mm 3.50 mm x 8, 12, 20, 28, 38 mm 4.00 mm x 8, 12, 20, 28, 38 mm 
-bare metal stents (Omega[®], Rebel[®])
 
 2.25 mm x 8, 12, 20, 28, 32, 38 mm 2.50 mm x 8, 12, 20, 28, 38 mm 3.00 mm x 8, 12, 20, 28, 38 mm 3.50 mm x 8, 12, 20, 28, 38 mm 4.00 mm x 8, 12, 20, 28, 38 mm
Antiplatelet regimen	-Dual antiplatelet therapy will be similar and administered for a similar duration after Synergy [®] II and BMS implantation. DAPT duration will be one month after percutaneous coronary intervention for stable angina and silent ischemia, or six months after percutaneous coronary intervention for acute coronary

	
syndrome, irrespective of the type of stent (Synergy[®] II or BMS[®]).
 
-Aspirin will be prescribed to all patients at an initial intra venous or oral loading dose of 150-300mg and at a maintenance dose of 75-100 mg orally daily, indefinitely. ADP P2Y₁₂ receptors inhibitors will be added to aspirin after percutaneous coronary intervention and maintained over 1 month (stable angina or silent ischemia) or 6months (acute coronary syndrome).
 
- Patients could be treated by different P2Y₁₂ inhibitors:
 
 - clopidogrel 300/600mg loading dose and 75mg/d OR - prasugrel 60mg loading dose and 5mg/d orally OR - ticagrelor 180mg loading dose and 90mg/bd orally 
The choice of ADP P2Y₁₂ receptors inhibitors is left to the physician's discretion but need to be determined before the randomization process.

Study design	
Randomized Clinical Trial (RCT)
 
Prospective, single blinded, randomized multicenter trial of 1,200 patients enrolled in approximately 40 international centers.
 
After diagnostic angiography demonstrating significant coronary artery disease requiring PCI and if the patients meet all the study inclusion criteria and none of the exclusion criteria, after signing the informed consent, they will be randomized 1:1 to:
 
 a) PCI using one or more Synergy[®] II (N=600), with DAPT including aspirin AND one P2Y₁₂ inhibitor (clopidogrel OR prasugrel OR ticagrelor), b) PCI using BMS (N=600), with DAPT including aspirin AND P2Y₁₂ inhibitor (clopidogrel OR prasugrel OR ticagrelor). 
Follow-up for all randomized subjects will continue for one year with an additional follow-up to 2 years.

Primary End Point	
-Composite measure of MACCEs: all-cause mortality, myocardial infarction, stroke and ischemia-driven target lesion revascularization (by PCI or CABG) at one year (with all randomized subjects having reached the one year follow-up).

Secondary end points	
 - Primary endpoint at 30 days,180 days and 2 years - All individual component of the primary endpoint at 30 days, 180 days, 1 year and 2 years: 
 -cardiac death -Myocardial Infarction (according to Third Universal Definition) -Stroke -Ischemia-driven target lesion revascularization (by PCI or CABG) - All revascularization (ischemia-driven and non-ischemia driven) at 30 days, 180 days, 1 year and 2 years: 
 -all target lesion revascularization (TLR) -all target vessel revascularization (TVR) -all non target vessel revascularization (non TVR) - complete revascularization at baseline procedure, anatomic and functional - Net benefit at 30 days, 180 days, 1 year and 2 years: association of composite events (all cause mortality, myocardial infarction, stroke, ischemia driven target lesion revascularization, and major bleedings). - Major bleeding complications (type 2, 3 and 5 BARC definition) at 30 days, 180 days,1 year and 2 years. (6) - Stent thrombosis according to the definition of ARC symptomatic or asymptomatic (definite + probable) at 30 days, 180 days, 1 year and 2 years. (5) - QoL, 12 months and 24 months - Depression scale at 12 months and 24 months - Cost effectiveness at 12 months
Pre-defined subgroup analyses	
 - Acute Coronary Syndrome vs non Acute Coronary Syndrome (stable angina and silent ischemia) - Patients \geq 85 years old - Women - Patients with type 2 diabetes mellitus

	- Patients with atrial fibrillation
Quality of life (QoL)	
Quality of life (QoL) will be assessed alongside the core clinical trial to evaluate the impact of the Synergy[®] II on a range of relevant quality of life (QoL) domains.
 
QoL and functional status will be assessed using a combination of generic and disease-specific measures selected to cover a broad range of health domains that may be affected by coronary artery disease, its treatment, and its complications. Mental health and depression will be assessed using the Geriatric Depression Scale. Health utilities will be assessed using the Euro QoL (EQ-5D 5L). These measures will be assessed using standardized, written questionnaires at baseline (prior to randomization), at 12 months and 24 months

Subject enrollment	A total of 1,200 subjects will be enrolled in approximately 40 international sites.
Subject follow up	Clinical follow-up at in-hospital, 30, 180 days, and one year, with an additional follow-up to 2years.
Treatment Strategies	
All subjects participating in this clinical trial will have informed consent obtained prior to randomization.
 
Inclusion Criteria (ALL must be present):
 
 - Patient is ≥ 75 years old - One or more significant coronary artery stenosis is/are present (defined as $\geq 70\%$ by visual assessment or $\geq 50\%$ with Fractional Flow Reserve < 0.80) or a left main coronary stenosis $\geq 50\%$ by visual assessment) suitable for PC I with one of the following present: 
 - Silent ischemia, 
 - stress-induced myocardial ischemia $\geq 10\%$ of myocardium in a asymptomatic patient or - stress-induced myocardial ischemia $< 10\%$ of myocardium AND FFR ≤ 0.80

	
or
 
 - Stable angina, in a patient with objective ischemia despite optimal medical therapy 
or
 
 - acute coronary syndrome including: unstable angina, non ST- and ST elevation myocardial infarction. 
- All patients must also sign informed consent as per local law and comply with all study process during follow up for at least one year.

Exclusion criteria	
 - The subject is not eligible for randomization if ANY of the following is present: 
 - Indication for myocardial revascularization by coronary artery bypass grafting, - Subjects unable to tolerate, obtain or comply with dual antiplatelet therapy for at least one month (stable angina or silent ischemia) or at least six month (acute coronary syndrome), - Subjects requiring additional surgery (cardiac or non-cardiac) within one month, - Non cardiac co-morbidities with life expectancy less than 1 year, - Prior hemorrhagic stroke, - Known allergy to aspirin or P2Y₁₂ inhibitors, - At least one contra indication to ALL the authorized P2Y₁₂ inhibitors at the requested dose (in case of contra indication to only one of two of the P2Y₁₂ inhibitors, the investigators are allowed to use the P2Y₁₂ inhibitors for which no allergy is known). - Silent ischemia <10% of the myocardium with FFR ≥0.80. - Participation in another clinical trial
Primary analytical population	The primary analysis of the composite endpoint of all-cause mortality, myocardial infarction, stroke and ischemia-driven target lesion revascularization will be performed on the intent-to-treat (ITT) population.
Statistical Method	The primary endpoint is a composite of all-cause mortality, myocardial infarction, stroke or ischemia-driven TLR with an

	
anticipated median follow-up of one year (efficacy).
 
The SENIOR study is powered to test the superiority of the Synergy[®] II with a relative 25% reduction of the primary endpoint
 
Assuming the following:
 
• primary endpoint event rate is 31% in control treatment arm at 1 year (interpolated from the most contemporary and accurate references)• minimum time to follow-up is 1 year• a constant dropout rate yielding 15% lost to follow-up at 1 year• two-sided alpha = 0.05• then a sample size population of 560 subjects per arm will provide 80% power to demonstrate superiority using a chi-square test comparing the event rates at 1 year from the Kaplan-Meier curves. The definitive total number will be 1.200 patients (600 in each arm).
--	--

1-Introduction

Coronary artery disease is a prevalent disease in patients ≥ 75 years with or without other risk factors. Aging of the population leads to frequent hospitalizations and significant medical and economic burden. However, there is currently no clear recommendation for how to treat specifically patients above 75 years suffering coronary artery disease (CAD). Patients above 75 years of age have been systematically underrepresented and highly selected in major clinical randomized trials underlying current recommendations for general population suffering stable or unstable CAD (1).

2-Background

Patients ≥ 75 years are a growing population among patients with acute coronary syndromes (ACS) or more stable situations. CAD is often diffuse and severe in this population. Age ≥ 75 years, is associated with a poor prognosis after CABG, so that PCI is often the best option for patients with ACS or for patients with stable angina/silent ischemia despite optimal medical treatment. In patients ≥ 75 years, PCI is often more difficult, because of lesion complexity, diffuseness and calcifications. Lesion length, small diameter of coronary arteries, bifurcated lesions are also common and are associated with an increased risk of in stent restenosis. Drug eluting stents (DES) have been shown to reduce angiographic and clinically restenosis in a wide variety of patients and lesions. The real rate of clinically relevant in stent restenosis in patients ≥ 75 years is difficult to determine, because this population is underrepresented in clinical trials evaluating DES. Furthermore, restenosis economical impact is far from being futile in this population. In their retrospective analysis based on the Medicare Standard Analytic File including all percutaneous coronary interventions performed in a year among unselected patients older than 65 years of age, Clark et al reported an independent cost of repeat revascularization of \$19,074 (95% CI 18,440 to 19,907) (2). In this analysis, among the

3,927 patients aged 75 years or above, a repeat revascularization was observed in 38% and a restenosis in 32% assuming that 85% of repeat revascularization procedures over the first year of follow-up are attributable to restenosis (2). In addition, patients with repeat revascularization were more likely to have experienced a MI during the follow-up. The estimated economic burden of restenosis was evaluated to be \$1,521 per patient for those \geq 85 years of age. It is important to note that in multivariate analysis, congestive heart failure, cerebrovascular disease and chronic renal failure among others, were significantly associated to an increase in total medical care and cardiovascular costs, those figures being highly prevalent in the patients \geq 75 years(2).

Therefore, all therapeutic devices that could reduce the rate of restenosis and recurrent revascularizations will have a major impact on rehospitalizations, and healthcare costs in that population. Unfortunately, because long-term dual antiplatelet therapy is associated with a significant high bleeding risk in patients \geq 75 years, bare metal stent are often the preferred choice for PCI despite a similar efficacy of DES in this population.

New generations DES appear to be both effective and safe. In their recent meta-analysis including 50,844 patients, Palmerini et al. reported a 1-year definite stent thrombosis significantly lower with cobalt-chromium everolimus eluting stents (CoCr-EES) than with baremetal stents (odds ratio [OR] 0.23, 95% CI 0.13–0.41) (3). The significant difference in stent thrombosis between CoCr-EES and bare-metal stents is evident as early as 30 days (OR 0.21, 95% CI 0.11–0.42) and is also significant between 31 days and 1 year (OR 0.27, 95% CI 0.08–0.74) after PCI. In randomized studies, CoCr-EES has the lowest rate of stent thrombosis within 2 years after implantation. The finding that CoCr-EES could reduce stent thrombosis compared with bare-metal stents, if confirmed in future randomized trials, would represent an important finding, especially for the patients \geq 75 years, but has never been evaluated specifically in this population.

First generations DES have been strongly criticized because of the small increased risk of late and very late stent thrombosis. Polymer hypersensitivity reactions, positive remodeling with late acquired malposition, delayed arterial healing, late stent fracture, and endothelial dysfunction are a few among the possible causes of the increased risk of very late stent thrombosis with first generations DES. The reduced rates of stent thrombosis with new generations of CoCr-EES stents may be attributed to the thromboresistant nature of the fluoropolymer or more rapid re-endothelialization, or both(3). Furthermore, an abluminal, fully biodegradable polymer-coated, thin struts DES, eluting everolimus such as the Synergy[®] II stent could therefore improve DES safety without reducing efficacy compared to BMS(4). In the recently published final 5-year report of the LEADERS (Limus Eluted From A Durable Versus ERodable Stent Coating) randomized, non inferiority trial, including 1,707 all comers patients, the biodegradable polymer-based DES (biolimus-eluting stents, BES) were compared to durable polymer DES (sirolimus eluting stents, SES). At 5 years, the BES was non-inferior to SES for the primary endpoint (186 [22.3%] vs. 216 [26.1%], rate ratio [RR]: 0.83 [95% confidence interval (CI): 0.68 to 1.02], p for non-inferiority <0.0001, p for superiority = 0.069); a composite of cardiac death, MI, or clinically indicated target vessel revascularization. Furthermore, BES was associated with a significant reduction in very late definite ST from 1 to 5 years (n = 5 [0.7%] vs. n = 19 [2.5%], RR: 0.26 [95% CI: 0.10 to 0.68], p = 0.003), corresponding to a significant reduction in ST-associated clinical events (primary endpoint) over the same time period (n = 3 of 749 vs. n = 14 of 738, RR: 0.20 [95% CI: 0.06 to 0.71], p = 0.005).

The ideal solution to reduce the unnecessary restenosis risk and the correlated rehospitalizations and the iatrogenic bleeding risk would be to treat patients ≥ 75 years with a DES and a short dual antiplatelet therapy similar to the one recommended with bare metal stents to conjugate the efficacy of newest DES and the safety of short duration of dual

antiplatelet therapy.

3-Study objective

The primary objective of this study is to establish the efficacy and safety of the everolimus eluting stent (Synergy[®] II, Boston Scientific), in association with a reduced duration of dual antiplatelet therapy, (comparable to the one recommended when using a BMS) in patients ≥ 75 years by demonstrating that compared to BMS (Omega[®], Rebel[®], Boston Scientific), treatment of coronary stenosis with Synergy[®] II will result in lower rates of the composite events of all-cause mortality, myocardial infarction, stroke or ischemia driven target lesion revascularization at an anticipated median follow-up duration of one year.

4-Study design

4-1 Study design

A total of 1,200 subjects will be enrolled in this study. This study will be a prospective, single blinded, randomized multicenter trial at approximately 40 international centers. Following diagnostic angiography demonstrating significant CAD requiring PCI and if the subject meets all the study entry criteria, he/she will be eligible for the study and randomized to: a) PCI using the Synergy[®] II stent or b) PCI with BMS stent with dual antiplatelet therapy of similar duration for both groups. Follow-up for all randomized subjects will continue for 1 year.

4-2 Subject Follow Up

All randomized subjects will be followed for at least 1-year period after baseline procedure. All randomized subjects will have a follow-up by telephone contact or office visit as described below:

- 30 days(+/- 5 days) visit: office visit

-
- 180 (+/-2weeks): telephone contact or office visit
 - 1 year visit(+ 4 weeks): office visit
 - 2 years (+/-4 weeks) visit: telephone contact or office visit.

4-3 Treatment strategy

All subjects participating in this randomized trial will have informed consent obtained after diagnostic angiography and prior to randomization. "Ad hoc" PCI is permitted as far as written informed consent has been obtained prior to the procedure. If more than one target lesion will be treated, all lesions must receive the treatment stent that has been assigned as per randomization (Synergy[®] II or Omega[®]/Rebel[®]).

5-Endpoints

5-1 Primary end point

The primary endpoint of this trial is the composite measure of MACCEs: all-cause mortality, myocardial infarction, stroke and ischemia driven target lesion revascularization (by PCI or CABG) at an anticipated median follow-up duration of 1 year (with all randomized subjects having reached the one year follow-up).

5-2 Secondary end points

- **Primary endpoints** at 30 days, 180 days and 2 years
- **All individual component of the primary endpoint** at 30 days, 180 days, 1 year, and 2 years:
 - Cardiac death
 - Myocardial Infarction (according to Third Universal Definition)
 - Stroke
 - Ischemia-driven target lesion revascularization (by PCI or CABG)

-All revascularization (ischemia-driven and non-ischemia driven) at 30 days, 180 days, 1 year and 2 years:

- all target lesion revascularization (TLR)

- all target vessel revascularization (TVR)

- all non target vessel revascularization (non TVR)

-complete revascularization at baseline procedure, anatomic and functional

-Net benefit at 30 days, 180 days, 1 year and 2 years: association of composite events (all-cause mortality, myocardial infarction, stroke, ischemia driven target lesion revascularization, and **major bleedings**).

-Major bleeding complications (type 2, 3 and 5 BARC definition) at 30 days, 180 days, 1 year and 2 years (6)

-Stent thrombosis according to the definition of definite and probable stent thrombosis according to ARC (symptomatic or asymptomatic) at 30 days, 180 days, 1 year and 2 years (5),

-QoL at 12 months and 24 months

-Depression scale at 12 months and 24 months

-Cost effectiveness at 12 months

6-Selection and withdrawal of the subjects

6-1 Subject population

Male and female subjects could be enrolled in the present study if they are 75 years old or older at the time of randomization. The randomized trial will enroll approximately 1,200 patients who need to meet ALL eligibility criteria and provide written informed consent prior to randomization. Each site should enroll a minimum of one randomized subject, and may not enroll more than a maximum of 120 randomized subjects.

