18.3 Monitor responsibilities

The Sponsor has appointed the CERC as Clinical Monitor for this study. CERC personnel are qualified by training and experience to oversee the conduct of the study. CERC will fulfill the responsibilities identified in its standard operating procedures (SOPs), available for review at CERC. These responsibilities include collecting and tracking data forms and trial compliance.

Under the supervision of the Sponsor and according to the Clinical Monitoring Plan agreed between CERC and the sponsor, monitors will conduct investigational site monitoring to ensure that all Investigators are in compliance with the regulatory requirements of the Standard ISO 14155 and the latest version of the Declaration of Helsinki, with the Clinical Investigation Plan and with the Investigator's Agreement.

The Investigator and his study team should be available during monitoring visit and possible audits.

19-Appendix: definitions, abbreviations and acronyms

19-1 Primary endpoint definition

19-1-1 Definition of Death

Death will be defined as cardiovascular, non-cardiovascular and from unknown reason.

- **Cardiovascular Death** includes sudden cardiac death, death due to acute myocardial infarction, death due to heart failure or cardiogenic shock, death due to ischemic or haemorrhagic stroke, death due to other cardiovascular causes, and death due to bleeding as follows:

- o **Sudden Cardiac Death** refers to death that occurs unexpectedly:

- § Witnessed and instantaneous without new or worsening symptoms

- § Witnessed within 60 minutes of the onset of new or worsening cardiac symptoms

§ Witnessed and attributed to an identified arrhythmia (e.g., captured on an electrocardiographic (ECG) recording or witnessed on a monitor by either a medic or paramedic)

§ Subjects unsuccessfully resuscitated from cardiac arrest

§ Subjects successfully resuscitated from cardiac arrest but who die without identification of a non-cardiac etiology (Post-Cardiac Arrest Syndrome)

§ Unwitnessed death or other causes of death (information regarding the subject's clinical status preceding death should be provided, if available)

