- Renal causes
- Gastrointestinal causes
- Infection (includes sepsis)
- Non-infectious (e.g., systemic inflammatory response syndrome (SIRS))

-
- o Malignancy (i.e., new malignancy, worsening of prior malignancy)
 - o Accidental/Trauma
 - o Suicide
 - o Non-cardiovascular system organ failure (e.g., hepatic failure)
 - o Non-cardiovascular surgery
 - o Other non-cardiovascular
- **Undetermined cause of death** refers to a death not attributable to one of the above categories of cardiovascular death or to a non-cardiovascular cause. *For this trial all deaths with undetermined causes will be included in the cardiovascular category.*

19-1-2 Definition of Acute Myocardial infarction(7)

The term acute myocardial infarction (MI) should be used when there is evidence of myocardial necrosis in a clinical setting consistent with acute myocardial ischaemia. Under these conditions any one of the following criteria meets the diagnosis for MI:

- Detection of a rise and/or fall of cardiac biomarker values [preferably cardiac troponin (cTn)] with at least one value above the 99th percentile upper reference limit (URL) and with at least one of the following:

Symptoms of ischaemia.

New or presumed new significant ST-segment–T wave (ST–T) changes or new left bundle branch block (LBBB).

Development of pathological Q waves in the ECG.

Imaging evidence of new loss of viable myocardium or new regional wall motion abnormality.

Identification of an intracoronary thrombus by angiography or autopsy.

-
- Cardiac death with symptoms suggestive of myocardial ischaemia and presumed new ischaemic ECG changes or new LBBB, but death occurred before cardiac biomarkers were obtained, or before cardiac biomarker values would be increased.
 - Percutaneous coronary intervention (PCI) related MI is arbitrarily defined by elevation of cTn values ($>5 \times$ 99th percentile URL) in patients with normal baseline values (\leq 99th percentile URL) or a rise of cTn values $>20\%$ if the baseline values are elevated and are stable or falling. In addition, either (i) symptoms suggestive of myocardial ischaemia or (ii) new ischaemic ECG changes or (iii) angiographic findings consistent with a procedural complication or (iv) imaging demonstration of new loss of viable myocardium or new regional wall motion abnormality are required.

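### The list of primary-endpoint components names cardiac death, but the death component of the composite is all-cause mortality, which is not named as an endpoint of its own

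*Protocol*

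**What the plan says.** The Protocol Summary gives the primary endpoint as "Composite measure of MACCEs: all-cause mortality, myocardial infarction, stroke and ischemia-driven target lesion revascularization (by PCI or CABG) at one year". Section 5-1 names the same four components. The Summary rows on objectives, analysis population and statistical method, and sections 3 and 12, also have all-cause mortality as the death component.

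Among the secondary endpoints, the Summary has the heading "All individual component of the primary endpoint at 30 days, 180 days, 1 year and 2 years". The items under it begin "cardiac death -Myocardial Infarction (according to Third Universal Definition) -Stroke" and end with ischaemia-driven TLR. Section 5-2 repeats the list, and its death item is again "Cardiac death".

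Appendix 19-1-1 classifies deaths differently: "Death will be defined as cardiovascular, non-cardiovascular and from unknown reason". It adds a rule for unclear causes: "For this trial all deaths with undetermined causes will be included in the cardiovascular category". The phrase cardiac death appears there when non-cardiovascular death is defined by exclusion, as death that is neither cardiac nor vascular. No criteria separate those two.

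**The concern.** A component table should let a reader take the composite apart. For that, any patient with a composite event by a given time must appear in at least one component at that time. Three of the four listed items match the composite and the death item does not. Because both lists carry the same item, the person writing the analysis has no correct version to fall back on.

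The composite mixes death with TLR. If it favours the drug-eluting stent through fewer TLRs, total mortality is the figure to set beside it, and cardiac death alone cannot supply it. Cardiac death also needs a judgement on cause, which all-cause mortality does not. The trial is single blind, and section 16 does not say that the events committee is blinded.

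**Working it through.** The plan gives no figure for this point, so the main check sets the passages side by side.

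**Step 1: does the list cover the composite?** Take a patient with a single event by the time point.

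| Only event | In the composite? | In a listed component? |
|---|---|---|
| MI, stroke or ischaemia-driven TLR | Yes | Yes, on its own line |
| Sudden cardiac death, or death from MI or heart failure | Yes | Yes, as cardiac death |
| Death from pulmonary embolism, aortic rupture or bleeding (cardiovascular in 19-1-1) | Yes | Not settled: no boundary between cardiac and vascular |
| Death of undetermined cause (cardiovascular in 19-1-1) | Yes | Not settled: no rule for cardiac |
| Death from infection, malignancy or trauma | Yes | No |

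Components may overlap, so their counts need not add up to the composite, but their union should equal it. With all-cause mortality as the death item it does. With cardiac death it falls short by every patient whose only event is a non-cardiac death. The gap recurs at all four time points (30 days, 180 days, 1 year, 2 years).

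**Step 2: is all-cause mortality listed elsewhere?** In sections 5-1 and 5-2 and the Summary it appears only inside the primary composite and inside net benefit, which adds major bleeding. Neither shows mortality alone.

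**Step 3: how many patients?** The document gives neither the death rate nor the non-cardiac share, so both are assumptions.

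- 8% one-year mortality: 600 × 0.08 = 48 deaths per arm. One third is 16 and one half is 24.
- 4% mortality: 600 × 0.04 = 24 deaths. One third is 8.
- 10% mortality: 600 × 0.10 = 60 deaths. One half is 30.

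The range is 8 to 30 per arm. Under these assumptions each figure is an upper bound, because a patient who dies of a non-cardiac cause may already have had a listed MI, stroke or TLR, and a fatal stroke counts under stroke. For scale, the design rate of 31% implies 0.31 × 600 = 186 control patients with a composite event under complete follow-up. Then 16/186 = 8.6% and 24/186 = 12.9%, again as upper bounds.

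**Step 4: does the sample size depend on it?** Section 12 compares 31% with 31% × 0.75 = 23.25%, with 15% dropout at one year and 560 per arm. With exponential event hazard λ and dropout hazard μ, the Greenwood variance of the one-year survival estimate S is S² × [λ/(λ+μ)] × [exp(λ+μ) − 1]/n.

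- Control: λ = −ln 0.69 = 0.3711, μ = −ln 0.85 = 0.1625, variance = 0.2334/560.
- Active: λ = −ln 0.7675 = 0.2646, same μ, variance = 0.1945/560.
- Standard error = √(0.4279/560) = 0.0276. 0.0775/0.0276 = 2.80, and 2.80 − 1.96 = 0.84, giving power of 80.1%.

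Simulation with 10,000 runs gave 80.6%. The stated 80% is reproduced, and nothing in it depends on the component list.

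**The case against.** The strongest reply is that the heading promises every component and all-cause mortality is one, so the protocol contradicts itself without excluding the analysis. Section 12 leaves the analyses to a statistical analysis plan that is not at hand. A reader might infer that all-cause mortality will never be analysed on its own. The document does not support that. It supports only that the protocol does not name it separately and that the list conflicts with its heading.

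A reader might also infer that cardiac death has no meaning in the protocol. That goes too far as well. Appendix 19-1-1 uses the term and describes plainly cardiac subtypes: sudden cardiac death, and death from infarction or from heart failure. What is missing is narrower: the line between cardiac and vascular, and the place of undetermined deaths.

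Nor are non-cardiac deaths invisible. They count in the primary composite and in net benefit at all four time points, the appendix classifies them, section 13.1.3 makes any event leading to death serious, and section 15 provides a safety board. An events committee reviews key endpoint-related events (section 16), so cause of death does not rest on site judgement alone, although the committee's blinding is not stated.

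These replies narrow the point but do not remove it. The protocol itself fixes the list, and the list is wrong against its heading. An analysis plan that follows the list inherits the error, and one that follows the heading departs from the list.

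**Conclusion.** The point holds as an internal contradiction in a secondary endpoint, present in both places where it is listed. Followed as written, the component analysis uses a narrower death endpoint than the composite does, and the boundary of that endpoint is incompletely specified. The comparison of the wording rests on no assumption. The size does: 16 to 24 patients per arm, or 8 to 30 over the wider range, are upper bounds on assumed mortality and assumed non-cardiac share, and neither input is in the document. The primary endpoint, its test and the sample size stand. The correction should be made because it decides whether the composite can be interpreted, but it does not threaten the primary analysis.

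**What to change.** In the Summary's secondary endpoints and in section 5-2, replace cardiac death with all-cause mortality. That alone resolves the contradiction.

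If a cause-specific death endpoint is wanted, list it on a separate line, not as a component of the primary endpoint. Either use cardiovascular death as 19-1-1 defines it, with undetermined deaths included, or define cardiac death there: which vascular deaths it leaves out and where undetermined deaths go. Further lines for cardiovascular and non-cardiovascular death are optional. The analysis plan should carry the same wording.

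The cost is one changed item in each of two lists, plus a short definition if cardiac death is kept. Deaths already count towards the primary endpoint and the appendix already classifies them, so no new data and no change in sample size follow.
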